## 2.9.4 Other safety data

### 2.9.4.1 Electrocardiogram (ECG)

Electrocardiogram (ECG) data will be listed. Listing will include date of assessment, position=supine, any new clinically significant abnormalities (yes/no), QTcF (Fridericia's correction), mean heart rate and mean PR, QT and QRS durations. Notable values and records outside of on-treatment period will be flagged.

Where ECG replicates are provided for an assessment, the average of the ECG parameters at that assessment will be used in the analyses.

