2.6 Risks and benefits

The risk to subjects in this trial may be minimized by compliance with the eligibility criteria and study procedures, and close clinical monitoring. There may be unforeseen risks with study treatment which could be serious.

The risk and benefit have been identified in the [[PKC412A2106](#)] and RATIFY' studies ([\[CPKC412A2301\]](#)).

The phase Ib study (A2106) investigated different doses and schedules of midostaurin in combination with daunorubicin and cytarabine induction and high-dose cytarabine consolidation therapy in 69 patients with newly-diagnosed AML. At the best tolerated dose of 50 mg b.i.d CRs occurred in 32/40 (80%) of all patients, 20/27 (74%) of FLT3-WT patients, and 12/13 (92%) of FLT3-mutant patients. One and 2-year overall survival (OS) for the patients with FLT3-mutant AML were 85% and 62%, respectively, and were comparable to those of the FLT3-WT subgroup (81% and 59%, respectively). These data were based on small numbers and were not stratified for type of FLT3 mutation (i.e. TKD vs ITD, ITD length, location, or allelic ratio) ([Stone et al 2009](#), [Stone et al 2012](#)).

With the recommended sequential treatment schedule (where midostaurin is started on day 8 after the completion of chemotherapy), AEs reported in $\geq 50\%$ of patients included

hematological AEs (thrombocytopenia, neutropenia, febrile neutropenia) and nausea, diarrhea, vomiting, pyrexia, hypokalemia, chills, and headache. The most frequent grade 3 and grade 4 AEs were hematological AEs (thrombocytopenia, neutropenia, febrile neutropenia, anemia, and leukopenia). Grade 3 non-hematological AEs reported in >10% of patients in either arm were those associated with GI toxicity (nausea, vomiting), increases in liver function test results (ALT, AST, bilirubin), electrolyte imbalance (hypocalcemia, hypokalemia, hypophosphatemia), and pyrexia, hypoxia, and device-related infection. One on-treatment death was reported in the study. The patient died due to fungal infection associated with multi-organ failure that was not considered to be related to study drug by the Investigator. AEs that led to discontinuation were reported for 8.8% of patients (5% with 50 mg b.i.d, and 14% with 100 mg b.i.d).

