6.3.2.3 Cardiac toxicity

For QTc interval >470 ms and ≤ 500 ms, check magnesium and potassium levels and correct any abnormalities. If possible, stop any medication, which may prolong the QTc interval. Decrease midostaurin to 50 mg once daily until QTc interval improves to ≤ 470 ms, and then resume midostaurin with 50 mg twice daily.

For QTc interval > 500 ms, immediately stop midostaurin, check magnesium and potassium levels and correct any abnormalities. If possible, stop any medication, which may prolong the QTc interval. Re-start with midostaurin 50 mg once daily if QTc interval is between >470 ms and ≤ 500 ms. Once QTc interval improves to ≤ 470 ms, resume midostaurin with 50 mg twice daily. If QTc interval remains > 470 ms for more than three weeks, discontinue midostaurin until QTc improves to < 470 ms, then resume midostaurin with 50 mg twice daily. Missed doses of midostaurin will not be made up.

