7.2.2.7 Cardiac assessment

7.2.2.7.1 Electrocardiogram (ECG)

A standard 12 lead ECG will be performed as indicated in [Table 7-1](#). All initial ECG assessment must be done **PRIOR** to the first dose of midostaurin.

Interpretation of the tracing must be made by a qualified physician and documented on the ECG CRF page. Each ECG tracing should be labeled with the study number, patient initials (where regulations permit), patient number, date, and kept in the source documents at the study site. Clinically significant abnormalities present when the patient signed informed consent should be reported on the Medical History CRF page. Clinically significant findings must be discussed with Novartis prior to enrolling the patient in the study. New or worsened clinically significant findings occurring after informed consent must be recorded on the Adverse Events CRF page.

For dose modifications for cardiac toxicity refer to [Section 6.3.2.3](#) for induction and consolidation, and [Section 6.3.3.3](#) for maintenance.

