10.5.3.4 Other safety data

Other safety data (including vital signs and weight) will be summarized and listed, notable values will be flagged, and any other information collected will be listed as appropriate.

ECG

A standard 12-lead ECGs including PR, QRS, QT and QTcF intervals will be obtained for each subject during the study. ECG data will be read and interpreted locally.

Listing will be provided with notable values flagged.

Vital signs

Data on vital signs will be tabulated and listed, notable values will be flagged.

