#### **2.9.3 Laboratory data**

Laboratory values are converted to the international system of units (SI). CTCAE Grade 0 will be assigned for all non-missing values not graded as 1 or higher. Grade 5 will not be used. For laboratory results where grades are not defined by CTCAE v4.03, results will be categorized as low/normal/high based on laboratory normal ranges.

The following summaries will be generated separately for key hematology and biochemistry by period and overall for the safety set:

- Shift tables by grade (or low/normal/high if grades not available) to compare baseline to the worst on-treatment value:
  - Hematology: Neutrophils (absolute) and platelets
  - Chemistry: Creatinine, total bilirubin, aspartate aminotransferase (AST), alanine aminotransferase (ALT) and alkaline phosphatase

Listing of all laboratory data (including urinalysis, coagulation, thyroid panel, pregnancy test etc.) will be provided with the corresponding CTCAE grades, if applicable, and the classifications relative to the laboratory normal ranges. Records outside of on-treatment period will be flagged.

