**Table 2-4 Notable criteria for ECG parameters**

Parameter	Notable low value	Notable high value
QTcF		New value of >450 and ≤ 480 ms New value of >480 and ≤ 500 ms New value of >500 ms Increase from baseline of >30 ms to ≤ 60 ms Increase from baseline of >60 ms
Heart rate	Decrease >25% from baseline and to a value <50 bpm	Increase >25% from baseline and to a value >100 bpm
PR	--	Increase >25% from baseline and to a value >200 ms New value of >200 ms
QRS	--	Increase >25% from baseline and to a value >120 ms New value of >120 ms

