### **6.2 Laboratory parameters derivations**

CTC grading for blood differentials is based on absolute values. However, this data may not be reported as absolute counts but rather as percentage of WBC.

If laboratory values are provided as ‘<X’ (i.e. below limit of detection) or ‘>X’, prior to conversion of laboratory values to SI unit, these numeric values are set to X.

The following rules will be applied to derive the WBC differential counts when only percentages are available for a xxx differential

$$\text{xxx count} = (\text{WBC count}) * (\text{xxx \%value} / 100)$$

Further derivation of laboratory parameters might be required for CTCAE grading. For instance, corrected calcium can be derived using the reported total calcium value and albumin at the same assessment using the following formula:

$$\text{Corrected Calcium (mg/dL)} = \text{Calcium (mg/dL)} - 0.8 [\text{Albumin (g/dL)} - 4]$$

In order to apply the above formula, albumin values in g/L will be converted to g/dL by multiplying by 0.1, calcium values in mmol/L will be converted to mg/dL by dividing by 0.2495. For calculation of laboratory CTC grades 0 and 1, the normal range for derived corrected calcium is set to the same limits (in mg/dL) as for calcium.

For missing Blood Urea Nitrogen (BUN) or urea values the following formulae will be applied:

$$\text{Urea (mg/dL)} = \text{BUN (mg/dL)} / 0.357$$

$$\text{BUN (mg/dL)} = \text{Urea (mg/dL)} / 2.1428$$

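### The QTcF criteria of SAP Table 2-4 only flag rows in a listing, so no planned table counts patients by measured QTcF; the AE tables fill that gap only in part

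*SAP*

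**What the plan says.** SAP 2.9.4.1 says "Electrocardiogram (ECG) data will be listed", with notable values flagged. Table 2-4 sets the criteria. For QTcF there are three bands (above 450 to 480 ms, above 480 to 500 ms, and "New value of >500 ms") and two rises from baseline (above 30 to 60 ms, and above 60 ms). There are further criteria for heart rate, PR and QRS. The ECG paragraph of Protocol 10.5.3.4 plans the same output: "Listing will be provided with notable values flagged".

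Neighbouring safety data are treated differently. LVEF is summarised as change from baseline to the worst on-treatment value, by period and overall (SAP 2.9.4.2). Vital signs are summarised by period and overall (SAP 2.9.4.4). Laboratory shift tables cover seven tests: "Hematology: Neutrophils (absolute) and platelets", plus creatinine, total bilirubin, AST, ALT and alkaline phosphatase (SAP 2.9.3).

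The AE route is separate. SAP 2.9.1 plans tables by preferred term and maximum severity, including AEs leading to discontinuation and to dose reduction or interruption. SAP 2.9.1.1 adds an AESI table. Protocol 7.2.2.7.1 says of ECGs: "New or worsened clinically significant findings occurring after informed consent must be recorded on the Adverse Events CRF page".

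**The concern.** Safety is the primary objective, and QTc prolongation has its own stepwise midostaurin rule both in induction and consolidation (Protocol 6.3.2.3) and in maintenance (6.3.3.3). The rule works at 470 and 500 ms and tells sites to "check magnesium and potassium levels and correct any abnormalities". The SAP defines patient-level QTcF criteria and then never counts patients against them. A flagged listing gives no numerator, no denominator and no comparison between periods.

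The study gives midostaurin to Day 28 rather than Day 21 as in RATIFY (Protocol 2.3) and has no upper age limit (2.2). Readers will therefore look for a measured QTc rate, above all in single-agent maintenance. As planned, they would have to count it from listing rows or rely on what sites chose to report as AEs.

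**Working it through.** **1. The plan's own precision figure.** Protocol 10.8 and SAP section 3 give a 95% probability of seeing at least one patient with an event of 1% true incidence when N = 300. Check: 1 − (1 − 0.01)^300 = 0.9510, as stated. With the 301 enrolled (SAP section 1) it is 0.9514. The size is thus justified by the ability to see events at about 1%. The point below is whether such an event, if it is a measured QTcF value, would be counted.

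**2. What the AE tables catch.** Under Protocol 8.1.1 an abnormal test result is an AE if it causes signs or symptoms, is clinically significant, needs therapy, or needs a change in study medication.

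- *QTc above 500 ms during midostaurin dosing.* Protocol 6.3.2.3 and 6.3.3.3 require midostaurin to be stopped, so the finding meets the AE definition and should be tabulated. The rows are preferred terms and CTCAE grades, however, not the bands of Table 2-4.
- *A rise above 60 ms that ends at or below 470 ms.* Take an assumed patient going from 400 to 465 ms. The rise is 465 − 400 = 65 ms, which meets the largest change criterion of Table 2-4. Since 465 is not above 470, no dose rule applies. Unless the investigator judges it clinically significant, or it meets another limb of the AE definition, it is not an AE and reaches no table.

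**3. Who could be evaluated.** In the ECG row of Table 7-1 (a table that did not extract cleanly) the marks fall at screening, induction C2D1 and C2D8, Days 1 and 8 of each consolidation cycle, Day 1 of each maintenance cycle, and end of treatment. None is shown at induction C1D8. Two limits follow.

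- A patient who goes to consolidation after one induction cycle has no scheduled on-treatment ECG in the induction period, so evaluable numbers there will be smaller.
- The induction and consolidation columns are headed as pre-dose, and midostaurin in those cycles runs from Day 8 to Day 28. Scheduled ECGs in those phases therefore come before that cycle's midostaurin. The maintenance ECGs fall within continuous dosing and are the most informative.

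**4. What a table would deliver.** The counts below are assumed. With no events among n patients, the exact two-sided 95% upper limit is 1 − 0.025^(1/n). Otherwise the Clopper-Pearson interval applies.

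| Assumed count | Rate | Exact 95% interval |
|---|---|---|
| 0 of 301 | 0% | 0 to 1.2% |
| 3 of 301 | 1.0% | 0.2% to 2.9% |
| 0 of 100 (a smaller evaluable group, assumed) | 0% | 0 to 3.6% |

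For the last row: 1 − 0.025^(1/100) = 0.036. Zero events means something quite different with 301 evaluable patients than with 100, which is why the number evaluable has to be shown.

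**5. Thresholds.** Protocol 5.3 excludes patients with QTc above 470 ms by Fridericia's formula, and 6.3.2.3 and 6.3.3.3 act at 470 and 500 ms. Table 2-4 cuts at 450, 480 and 500 ms. Its band from above 450 to 480 ms therefore mixes patients on both sides of 470 ms, and the flags cannot be read against the protocol's own threshold.

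**The case against.** The primary endpoint is AE-based: AEs, Grade 3 and 4 AEs, SAEs, AEs leading to discontinuation, and deaths. The SAP follows the protocol in listing ECGs, and its laboratory shift tables go beyond Protocol 10.5.3.3, which is marked not applicable. QTc findings that changed treatment should reach the AE tables. The table shells and the retrieval sheet that defines the AESIs are separate documents that were not available, so a further ECG table cannot be ruled out. All of this stands. It narrows the point without removing it: the SAP text says listed for ECG and summarised for its neighbours, and if a shell already holds the table, the text should say so.

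A reader might infer something stronger: that no planned table counts patients with QTc above 500 ms, or with Grade 3 or 4 electrolyte or hemoglobin abnormalities. The documents do not support that.

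- Such events reported as AEs are counted by preferred term and maximum severity. Protocol 8.1.1 gives a hematologic abnormality needing transfusion as an example of an AE.
- The earlier Grade 3 electrolyte events and Grade 3 and 4 anemia in Protocol 2.6 are themselves AE data, so the like-for-like comparison is the planned AE table.
- SAP 6.2 says "corrected calcium can be derived using the reported total calcium value and albumin at the same assessment" and presents this as an instance of a derivation that might be needed for grading. It does not commit the plan to a calcium table.
- Under Table 7-1 and Protocol 7.2.2.5, chemistry after baseline is done when justified by a treatment-related AE or SAE, or at the physician's discretion. Hematology is also taken for response assessments. A wider shift table would describe selectively tested patients. The same limit applies to the chemistry tests already tabulated, so it is a reason for caution rather than a bar.

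**Conclusion.** The point holds for QTcF. Both documents give measured ECG values a listing only, and the AE tables neither separate the Table 2-4 categories nor catch changes that triggered no action and were not judged significant. It is a gap in descriptive reporting of a toxicity that has its own treatment rule, in a study whose primary objective is safety. It has no bearing on sample size, power or alpha, because no hypothesis is tested (Protocol 10.4.2).

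The number of patients who escape the AE tables cannot be derived from the documents. The intervals above show only the precision that a count would have, with 301 as the largest possible denominator. The conclusion assumes that the unseen table shells match the SAP text and that the ECG row of Table 7-1 has been read correctly. The mismatch between the SAP bands and the 470 ms threshold is plain on the face of the documents. For hemoglobin and electrolytes, adding shift tables is a matter of choice.

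**What to change.** In SAP 2.9.4.1, add a table of n (%) of patients meeting each Table 2-4 criterion at any on-treatment ECG, unscheduled ECGs included, by period and overall.

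- *Denominator:* patients with at least one on-treatment ECG in that period, and also a baseline ECG for change criteria. Show the number evaluable beside each percentage.
- *Counting:* each patient once per criterion per period. State that the closest-to-target selection of SAP 2.1.5 does not apply here, since it could discard a notable unscheduled ECG. State what *new value* means relative to baseline. If it requires a baseline outside the band, a baseline ECG is needed there too.
- *Reading:* add a note on the induction C1D8 gap and the pre-dose timing in induction and consolidation.
- *Thresholds:* reconcile the Table 2-4 bands with the 470 ms threshold of Protocol 5.3, 6.3.2.3 and 6.3.3.3, or explain why reporting and protocol thresholds differ.

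Optionally, add hemoglobin, potassium, magnesium, corrected calcium and phosphorus to the shift tables of SAP 2.9.3, with the number of patients having a post-baseline value and a statement that testing was selective.

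The cost is one extra table from data already collected. The latest SAP version in the document history is dated after database lock, so the addition should be labelled as made after lock.

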**Table 2-4 Notable criteria for ECG parameters**

Parameter	Notable low value	Notable high value
QTcF		New value of >450 and ≤ 480 ms New value of >480 and ≤ 500 ms New value of >500 ms Increase from baseline of >30 ms to ≤ 60 ms Increase from baseline of >60 ms
Heart rate	Decrease >25% from baseline and to a value <50 bpm	Increase >25% from baseline and to a value >100 bpm
PR	--	Increase >25% from baseline and to a value >200 ms New value of >200 ms
QRS	--	Increase >25% from baseline and to a value >120 ms New value of >120 ms

### 2.9.4.2 Cardiac imaging

The left ventricular ejection fraction (LVEF) data will be summarized for change from baseline to the worst on-treatment value by period and overall for the safety set. A listing will be provided showing the imaging method (multi gated acquisition scan (MUGA) or echocardiogram), date of assessment, LVEF percentage, the overall interpretation (normal, clinically insignificant abnormality or clinically significant abnormality) and the corresponding ejection fraction CTCAE v4.03 grades. Records outside of on-treatment period will be flagged.

Grades:

- Grade 0: Non missing value below Grade 2
- Grade 1: NA
- Grade 2: 50-40% or 10-19% drop from baseline i.e.
  - $40\% \leq \text{LVEF} \leq 50\%$  or  $-20\% < \text{absolute change from baseline} \leq -10\%$
- Grade 3: 39-20% or ≥20% drop from baseline i.e.
  - $20\% \leq \text{LVEF} < 40\%$  or  $\text{absolute change from baseline} \leq -20\%$
- Grade 4: <20% i.e.
  - $\text{LVEF} < 20\%$

#### 2.9.4.3 Chest X-ray

Chest x-ray data will be listed showing date of assessment and the overall interpretation (normal, clinically insignificant abnormality or clinically significant abnormality). Records outside of on-treatment period will be flagged.

#### 2.9.4.4 Vital signs

Vital signs (height, weight, body surface area, temperature, position, pulse and systolic/diastolic blood pressure) will be summarized by period and overall for the safety set. Listings will be provided with notable values and records outside of on-treatment period flagged.

**Table 2-5 Notable criteria for vital signs**

Vital sign (unit)	Notable low value	Notable high value
Weight (kg)	decrease $\geq$ 10% from baseline	increase $\geq$ 10% from baseline
Body temperature (°C)	--	$\geq$ 39.1
Pulse rate (bpm)	$\leq$ 50 and decrease from baseline of $>25\%$	$\geq$ 100 and increase from baseline of $>25\%$
Systolic blood pressure (mmHg)	$\leq$ 90 and decrease from baseline of $\geq 20$	$\geq$ 180 and increase from baseline of $\geq 20$
Diastolic blood pressure (mmHg)	$\leq$ 50 and decrease from baseline of $\geq 15$	$\geq$ 105 and increase from baseline of $\geq 15$

#### 2.9.4.5 ECOG performance status

ECOG performance status data will be listed. Records outside of on-treatment period will be flagged. Baseline summary will be provided as part of the demographics table.

**Table 2-6 ECOG Performance Status**

Grade	ECOG
0	Fully active, able to carry on all pre-disease performance without restriction
1	Restricted in physically strenuous activity but ambulatory and able to carry out work of a light or sedentary nature, e.g. light house work, office work
2	Ambulatory and capable of all self-care but unable to carry out any work activities. Up and about more than 50% of waking hours
3	Capable of only limited self-care, confined to bed or chair more than 50% of waking hours
4	Completely disabled. Cannot carry on any self-care. Totally confined to bed or chair
5	Dead

#### 2.10 Pharmacokinetic endpoints

Not applicable.

## 2.11 PD and PK/PD analyses

Not applicable.

## 2.13 Biomarkers

Not applicable.

## 2.14 Other Exploratory analyses

[REDACTED] resource utilization will be used to evaluate the impact on symptom burden, overall quality of life and change in status of a patient's overall satisfaction with.

The safety set will be used for analyzing [REDACTED] resource utilization data unless otherwise specified.

11. **What is the primary purpose of the study?** (check all that apply)

113. *Leptodora* (Leptodora) *hirsutissima* (L.) Schlecht. (1854) 113. *Leptodora* (Leptodora) *hirsutissima* (L.) Schlecht. (1854)

© 2013 Pearson Education, Inc.

© 2013 Pearson Education, Inc.

Digitized by [contact]

For more information, contact the Office of the Vice President for Research and Economic Development at [contact] or [[contact]](mailto:[contact]).

1. **What is the primary purpose of the study?** (Please select one)

© 2019 Pearson Education, Inc.

10 of 10 pages

For more information, contact the Office of the Vice President for Research and Economic Development at [contact] or [[contact]](mailto:[contact]).

100

For more information, contact the Office of the Vice President for Research and Economic Development at [contact] or [[contact]](mailto:[contact]).

ANSWER

Digitized by [contact]

© 2019 Pearson Education, Inc.

For more information, contact the Office of the Vice President for Research and Economic Development at [contact] or [[contact]](mailto:[contact]).

A horizontal bar chart consisting of 15 black bars of varying lengths. The bars are arranged in a descending order of length from left to right. The first bar is the longest, and the last bar is the shortest. There are several very short bars scattered throughout the sequence.

### 2.14.3 Resource utilization

Descriptive statistics will be used to summarize resource utilization, e.g. the reason for hospitalization due to AE or not, if number of hospital days by facility/ward type and discharge status used during hospital stay(s). Listings will flag records outside of the on-treatment period.

## 2.15 Interim analysis

No formal interim analysis is planned for this study. Analyses may be performed periodically (e.g. annually), if needed, to fulfill regulatory requests, safety updates or for publication purposes.

### 3 Sample size calculation

Approximately 300 patients will be enrolled in this study. The planned sample size is based on the average expected accrual rate (17 patients per month) and the planned recruitment duration (18 months) of the trial. The actual sample size may differ from this planned number. A sample size of 300 patients provides a 95% probability of observing at least one patient with an adverse event (AE) assuming a true probability of occurrence of 1%.

Table 3-1 provides probabilities to detect at least one patient with an AE for different sample sizes and different true AE incidences.

**Table 3-1 Probability to detect at least one patient with an AE for different sample sizes and different true AE incidences**

Incidence of an adverse event	Sample size		
	N=200	N=250	N=300
0.4%	0.5514	0.6329	0.6995
0.5%	0.6330	0.7144	0.7777
0.6%	0.6999	0.7779	0.8356
0.8%	0.7994	0.8657	0.9102
1.0 %	0.8660	0.9189	0.9510
1.3%	0.9270	0.9620	0.9803

